#### 7.1.4 Relationship of an Adverse Event to the Study Drug

Investigators will classify the relationship of an adverse event to the study drug as follows:

- Definitely related:** An adverse event that is due to use of the study drug. The adverse event cannot be reasonably explained by an alternative explanation, eg, concomitant drug(s), concomitant disease(s). The temporal relationship is very suggestive.
- Probably related:** An adverse event that can be reasonably attributed to the use of the study drug. An alternative explanation is less likely, eg, concomitant drug(s), concomitant disease(s). The temporal relationship is suggestive.
- Unlikely related:** An adverse event for which an alternative explanation is more likely, eg, concomitant drug(s), concomitant disease(s), and/or the temporal relationship suggests that a causal relationship is unlikely.
- Not related:** An adverse event that is not related to the use of the study drug.

If the investigator determines that an adverse event is unlikely to be or not be related to the study drug, the investigator will determine whether the adverse event is most likely to be related to the surgical procedure, opioid use, or something else.

#### 7.1.5 Serious Adverse Events

For recording a serious adverse event, the study period is defined for each patient as described in [Section 7.1.2.4](#). Serious adverse events occurring in a patient after the end of the follow-up period should be reported to the sponsor, if the investigator becomes aware of them, following the procedures described in [Section 7.1.5.3](#).

##### 7.1.5.1 Definition of a Serious Adverse Event

A serious adverse event is any untoward medical occurrence that, at any dose, has the following characteristics:

- results in death
- is life-threatening

NOTE: An adverse event or adverse reaction is considered life-threatening if, in the opinion of either the investigator or sponsor, its occurrence places the patient at immediate risk of death. It does not include an event that, had it occurred in a more severe form, might have caused death.

- requires inpatient hospitalization or prolongation of existing hospitalization

NOTE: Any hospital admission with at least 1 overnight stay will be considered an inpatient hospitalization. An emergency room visit without hospital admission will not be recorded as a serious adverse event according to this criterion. Admission to the hospital for social or situational reasons (ie, no place to stay, lives too far away to come for

Innocoll

Clinical Study Protocol With Amendment 02

Study INN-CB-024

Controlled Study-Postsurgical Analgesia

hospital visits) will not be considered inpatient hospitalization. An elective hospital admission to treat a condition present before exposure to the study drug, or a hospital admission for a diagnostic evaluation of an adverse event, **does not** qualify the condition or event as a serious adverse event.

- results in permanent (persistent) disability/incapacity
- if a patient exposed to the study drug gives birth to a child with congenital anomaly or birth defect
- is an important medical event

Medical and scientific judgment should be exercised in deciding whether it is appropriate to consider other situations serious, such as important medical events that may not be immediately life-threatening or result in death or hospitalization, but which may jeopardize the patient or may require intervention to prevent one of the other outcomes listed in the definitions above.

Examples of such events are intensive treatment in an emergency room or at home for allergic bronchospasm, blood dyscrasias, or convulsions that do not result in hospitalization.

An adverse event that does not meet any of the criteria for seriousness listed above will be regarded as a nonserious adverse event.

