### **3.4 Stopping Rules for the Study**

Innocoll reserves the right to discontinue the study for safety or administrative reasons at any time.

The study will be stopped, until further benefit-risk evaluation is made, if 2 patients require removal of the INL-001 implants due to suspected systemic bupivacaine toxicity as outlined below in [Section 4.3.2](#).

During the conduct of the study, serious adverse events will be reviewed (see [Section 7.1.5](#)), as they are reported from the investigational centers, to identify safety concerns.

The study may also be terminated by the sponsor for any reason at any time. For example, the sponsor could terminate the study in the event of:

- new toxicologic or pharmacologic findings or safety issues from any source (eg, other clinical studies, postmarketing experience) that invalidate the earlier positive benefit-risk assessment
- discontinuation of the development of the investigational medical product

If the entire study is stopped or if elements of the study are stopped, the patients whose participation is terminated early will be monitored according to withdrawal criteria and procedures (see [Section 4.3](#)).

If the study is terminated prematurely, investigator(s) will inform their patients and arrange their appropriate follow-up.

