#### 7.1.5.3 Reporting a Serious Adverse Event

##### 7.1.5.3.1 Investigator Responsibility

To satisfy regulatory requirements, all serious adverse events that occur during the study, regardless of the assessed relationship to study drug treatment, must be reported to the sponsor by the investigator within 24 hours after the investigator becomes aware of it. Completing the serious adverse event form and reporting the serious adverse event must not be delayed, even if all the information is not available. The investigator does not need to actively monitor patients for adverse events once the study has ended.

The serious adverse event form will be sent to the contract research organization (CRO) and sponsor representatives.

The following information will be provided to record the adverse event accurately and completely:

- study number
- investigator and investigational center identification

Innocoll

Clinical Study Protocol With Amendment 02

Study INN-CB-024

Controlled Study-Postsurgical Analgesia

- patient number
- start date and detailed description of adverse event
- investigator's assessment of the relationship to study drug

Additional information may include:

- age and sex of patient
- date of implantation
- action taken
- outcome, if known
- severity
- explanation of assessment of relationship to study drug
- concomitant medication (including doses, routes of administration, and regimens) and treatment of the event
- pertinent laboratory or other diagnostic test data
- medical history
- results of dechallenge/rechallenge, if known
- for an adverse event resulting in death
  - cause of death (whether or not the death was related to study drug)
  - autopsy findings (if available)

Healing of the surgical wound will be assessed throughout the study and if there is a wound-related event, it will be recorded as such.

Each report of a serious adverse event will be reviewed and evaluated by the investigator and the sponsor to assess the nature of the event and the relationship of the event to the study drug, study procedures, and underlying disease.

Additional information (follow-up) about any serious adverse event unavailable at the time of initial reporting should be provided by the investigator within 24 hours of the time it becomes known.

The investigator must ensure the Institutional Review Board (IRB) is also informed of the event, in accordance with national and local regulations.

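### The serious adverse event definition counts any overnight admission as hospitalization but excludes admissions to investigate an adverse event, so a new event that meets no other criterion would be classed nonserious

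*Protocol*

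**What the plan says.** Protocol Section 7.1.5.1 lists the seriousness criteria. One is that the event "requires inpatient hospitalization or prolongation of existing hospitalization". The note under that criterion begins with a general rule: "Any hospital admission with at least 1 overnight stay will be considered an inpatient hospitalization". It then deals with four kinds of contact:

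- an emergency room visit without admission, which is not serious under this criterion;
- a social or situational admission, which is not counted as inpatient hospitalization;
- an elective admission to treat a condition that predates exposure to study drug;
- "or a hospital admission for a diagnostic evaluation of an adverse event".

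The last two are said not to "qualify the condition or event as a serious adverse event".

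The section closes with a default: "An adverse event that does not meet any of the criteria for seriousness listed above will be regarded as a nonserious adverse event". Two processes depend on the result. Under Section 7.1.5.3.1, a serious event "must be reported to the sponsor by the investigator within 24 hours after the investigator becomes aware of it". Section 3.4 says: "During the conduct of the study, serious adverse events will be reviewed".

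**The concern.** The overnight-stay sentence attaches no condition about why the patient was admitted. The diagnostic exclusion attaches no condition about how long the patient stayed or when the event began. The two overlap on one case: an overnight admission, after study drug has been placed, to find out what is causing a new adverse event.

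That case is plausible in this trial. Patients go home on day 4. They then have one telephone contact on day 7 and clinic visits on days 15 and 30 (Table 1), so a readmission is one way a late event could come to light. Section 7.1.6 names two safety areas of special interest, systemic bupivacaine toxicity and wound healing, and both include signs that could prompt an admission for investigation.

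At stake are the classification of such an event, the speed with which the sponsor hears of it, and consistency across up to 8 centers. One site could follow the overnight rule and another the exclusion.

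**Working it through.** The protocol states no figure on this point and no formula applies. The check sets the clauses side by side and follows one case through them.

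**The case.** A patient is discharged on day 4, develops a new adverse event, and is admitted overnight for investigation. The event is not life-threatening or disabling, and the investigator does not judge it an important medical event.

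1. *Overnight rule (7.1.5.1).* The stay is an inpatient hospitalization, so the hospitalization criterion is met and the event is serious.
2. *Diagnostic exclusion (7.1.5.1, same note).* The admission was for diagnostic evaluation of an adverse event, so it does not make the event serious.
3. *Other criteria (7.1.5.1).* Death, life-threatening, disability and birth defect do not apply. Important medical event rests on judgment: "Medical and scientific judgment should be exercised in deciding whether it is appropriate to consider other situations serious". In this case it has not been invoked.
4. *Default (7.1.5.1).* If step 2 prevails over step 1, no criterion is met and the event is nonserious.
5. *Consequences.* The 24-hour report (7.1.5.3.1), the expectedness and SUSAR provisions (7.1.5.2 and 7.1.5.3.2) and the event review in 3.4 all apply to serious events. The event enters none of them. It is still recorded in source documents and the CRF under 7.1.2.4.

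**Comparing the four exclusions.**

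- The emergency room visit involves no admission, so it does not meet the overnight rule.
- Social admissions are taken out of the definition of inpatient hospitalization, so the rule and the exclusion agree.
- Elective admissions are limited to conditions that existed before exposure, so a new event is not affected.
- Diagnostic admissions are neither taken out of the definition nor limited to earlier conditions. An overnight work-up remains an inpatient hospitalization under the note and is still said not to qualify.

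**Comparing with the important-medical-event examples.** These include convulsions treated intensively in an emergency room without hospitalization. An event handled without admission is thus a listed example of a serious event, while an overnight admission to investigate an event is expressly denied that effect. An investigator could still use the important-medical-event criterion in the second situation, but the text does not point there.

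**The case against.** The strongest reply is that the note is a rule followed by its exceptions, and exceptions always cut into a rule. Social and elective admissions can also run overnight, and nobody proposes to remove those exclusions. This has force: the wording can be read as a deliberate carve-out. It does not remove the problem, because on that reading the carve-out itself makes a new post-implant event needing overnight work-up nonserious by default.

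A reader might infer more than the documents support:

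- *That all work-up admissions drop out of expedited reporting.* They do not. The exclusion sits in the note to the hospitalization criterion and only stops the admission itself from conferring seriousness. An event that is life-threatening, disabling or an important medical event is still serious. An admission to treat an infection is not an admission for diagnostic evaluation.
- *That early toxicity is affected.* Prolongation of an existing stay remains a criterion, and patients are domiciled for at least 72 hours. In the hernia study in Section 1.4.2, median time to peak was 3.03 hours and mean half-life 18.95 hours, so 72 hours is 72 / 18.95 = 3.8 half-lives. If abdominoplasty is similar, toxicity would be expected mainly before discharge.
- *That serious-event review is the only safety oversight.* Section 3.4 also has a stopping trigger based on two implant removals. Section 4.3.1 requires the sponsor to be told of patients considered for withdrawal because of adverse events. Section 7.1.6.2 always records admission for wound infection as an adverse event. Section 7.1.2.4 refers to a Safety Monitoring Plan that is not shown. None of the visible provisions replaces a 24-hour report for a readmitted patient who stays in the study with implants in place. The committee in Section 5.11 deals only with sample size.
- *That a large share of serious events would be lost.* The program history gives 16 patients with serious events and 892 who received implants: 16 / 892 = 1.8%, or about 6.5 of 360. It is tempting to subtract a few work-up admissions from that. No document gives their number, the definition of seriousness behind the 16 is not stated, and the 16 include placebo or other comparator patients who may fall outside the 892. If the same exclusion applied then, the 6.5 already omits them.

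**Conclusion.** The concern holds in a limited form. Section 7.1.5.1 gives two answers for an overnight admission to investigate a new post-implant event. Under the exclusion, such an event is nonserious unless another criterion is met, and it then falls outside 24-hour reporting, SUSAR assessment and the Section 3.4 review.

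The conclusion assumes that a site applies the exclusion as written and that the Safety Monitoring Plan does not correct it. The size of the effect cannot be estimated from the documents, and no claim that the serious event rate will be understated by a given amount is supported. Overall adverse event capture and the efficacy analyses are unaffected. The change should still be made, because it concerns how quickly the sponsor learns of a readmission and is easy to put right.

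**What to change.** Delete the words "or a hospital admission for a diagnostic evaluation of an adverse event" from the note in Section 7.1.5.1. Alternatively, limit them to admissions without an overnight stay, or to conditions present before exposure. Keep the exclusions for social admissions and for elective admissions for pre-existing conditions. The overnight-stay rule then governs every overnight admission prompted by a new adverse event. Check that the Safety Monitoring Plan uses the same definition.

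The cost is one short amendment and, as a small downside, a few more serious adverse event reports. Sample size, visit schedule and analysis do not change.

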#### 7.1.5.2 Expectedness

A serious adverse event that is not included in the IB under reference safety information (RSI) for expedited reporting purposes by its specificity, severity, outcome, or frequency is considered an unexpected adverse event. This may also be determined using the product-prescribing information when it becomes available.

For the purpose of reporting a SUSAR, the edition of the IB at the time of occurrence of the SUSAR applies.

#### 7.1.5.3 Reporting a Serious Adverse Event

##### 7.1.5.3.1 Investigator Responsibility

To satisfy regulatory requirements, all serious adverse events that occur during the study, regardless of the assessed relationship to study drug treatment, must be reported to the sponsor by the investigator within 24 hours after the investigator becomes aware of it. Completing the serious adverse event form and reporting the serious adverse event must not be delayed, even if all the information is not available. The investigator does not need to actively monitor patients for adverse events once the study has ended.

The serious adverse event form will be sent to the contract research organization (CRO) and sponsor representatives.

The following information will be provided to record the adverse event accurately and completely:

- study number
- investigator and investigational center identification

Innocoll

Clinical Study Protocol With Amendment 02

Study INN-CB-024

Controlled Study-Postsurgical Analgesia

- patient number
- start date and detailed description of adverse event
- investigator's assessment of the relationship to study drug

Additional information may include:

- age and sex of patient
- date of implantation
- action taken
- outcome, if known
- severity
- explanation of assessment of relationship to study drug
- concomitant medication (including doses, routes of administration, and regimens) and treatment of the event
- pertinent laboratory or other diagnostic test data
- medical history
- results of dechallenge/rechallenge, if known
- for an adverse event resulting in death
  - cause of death (whether or not the death was related to study drug)
  - autopsy findings (if available)

Healing of the surgical wound will be assessed throughout the study and if there is a wound-related event, it will be recorded as such.

Each report of a serious adverse event will be reviewed and evaluated by the investigator and the sponsor to assess the nature of the event and the relationship of the event to the study drug, study procedures, and underlying disease.

Additional information (follow-up) about any serious adverse event unavailable at the time of initial reporting should be provided by the investigator within 24 hours of the time it becomes known.

The investigator must ensure the Institutional Review Board (IRB) is also informed of the event, in accordance with national and local regulations.

#### **7.1.5.3.2 Sponsor Responsibility**

If a SUSAR is believed to be related to the study drug or study procedures, the sponsor will take appropriate steps to notify all investigators participating in the study and the appropriate competent authorities (and IRB, as appropriate).

In addition to notifying the investigators and competent authorities (and IRB, as appropriate), other action may be required, including:

Innocoll

Clinical Study Protocol With Amendment 02

Study INN-CB-024

Controlled Study-Postsurgical Analgesia

- altering existing research by modifying the protocol
- discontinuing or suspending the study
- modifying the existing consent form and informing all study participants of new findings
- modifying listings of expected toxicities to include adverse events newly identified as related to treatment with INL-001

#### 7.1.6 Protocol-defined Adverse Events and Safety Assessments of Special Interest

There are 2 specific safety areas of interest for this study, systemic bupivacaine toxicity and wound healing. Signs and symptoms potentially indicative of systemic bupivacaine toxicity and signs and symptoms related to healing of the surgical wound will be evaluated at specified time points using the lists below. Signs and symptoms will be assessed and recorded as described above for adverse events in general. In addition, wound grading will be performed at specified time points using the Southampton Wound Grading System ([Bailey et al 1992](#)).

##### 7.1.6.1 Assessment of Signs and Symptoms Potentially Indicative of Systemic Bupivacaine Toxicity

Patients will be specifically queried and assessed by the investigator/subinvestigator (physician) for these signs and symptoms potentially indicative of bupivacaine toxicity at specified time points after implantation of study drug using the following list of signs and symptoms (see [Table 1](#)).

Have you had any of the following since we last spoke?

- respiratory difficulty
- change in level of consciousness
- restlessness
- anxiety
- difficulty speaking or being understood
- lightheadedness
- numbness and tingling of the mouth and lips
- metallic taste
- tinnitus (ringing in ears)
- dizziness
- changes in your vision
- tremors
- depression
- drowsiness

If a patient reports any of the above signs and symptoms, they will be assessed as to whether they qualify as adverse events and, if so, recorded as noted previously regarding adverse events. If the investigator determines that the patient experienced systemic bupivacaine toxicity, this will be recorded as an adverse event.

If any of these signs or symptoms are assessed (and recorded) as an adverse event(s), the severity of each adverse event must be recorded according to CTCAE (see [Section 4.3.2](#)).

Innocoll

Clinical Study Protocol With Amendment 02

Study INN-CB-024

Controlled Study-Postsurgical Analgesia

### 7.1.6.2 Wound Healing

The following signs and symptoms associated with wound healing will be queried and assessed by the investigator/subinvestigator (physician) at specified time points after implantation of study drug (see [Table 1](#)):

- **purulent discharge or leakage of fluid from the site**
- pain or soreness in addition to the discomfort experienced following the operation
- redness or inflammation spreading from the edges of the wound
- warmth in the area around the wound
- swelling in the area around the wound
- **separation of the edges of any part of the wound**
- **had been seen by a health care provider about the wound**
- **had been prescribed nonprophylactic antibiotics for an infection in the wound**
- **had been admitted to a hospital with an infection of the surgical wound**

If a patient reports any of the above signs and symptoms, which are shown in **bold text**, they will be recorded as adverse events related to the surgical site. If a patient reports any of the other (not bolded) signs and symptoms, they will be assessed as to whether they qualify as adverse events and, if so, recorded as noted previously regarding adverse events (see above in Section 7.1).

### 7.1.6.3 Wound Grading

At 72 hours posttreatment, day 15, and day 30 the investigator/subinvestigator (physician) will complete the Southampton Wound Grading System. Investigator judgment will be used to determine if a finding is an adverse event. If an adverse event is identified during completion of this assessment that was not previously identified through the wound healing assessment, it will be assessed and recorded according to the adverse event criteria defined above.

Innocoll

Clinical Study Protocol With Amendment 02

Study INN-CB-024

Controlled Study-Postsurgical Analgesia

Wound healing grade and appearance will be assessed as follows:

Grade	Appearance
0	Normal healing
I Normal healing with mild bruising or erythema:	
a	Some bruising
b	Considerable bruising
c	Mild erythema
II Erythema plus other signs of inflammation:	
a	At one point
b	Around sutures
c	Along wound
d	Around wound
III Clear or haemoserous discharge:	
a	At one point only ( $\leq 2$ cm)
b	Along wound ( $> 2$ cm)
c	Large volume
d	Prolonged ( $> 3$ days)
	Major complications
IV Pus:	
a	At one point only ( $\leq 2$ cm)
b	Along wound ( $> 2$ cm)
V Deep or severe wound infection with or without tissue breakdown; haematoma requiring aspiration	

